2.3.2 KNOWN POTENTIAL BENEFITS

There is no additional direct benefit to the subjects participating. The results of this study may potentially benefit to future patients and their peers on dialysis. If individual participants experience improvement in UF-related cardiovascular risk or symptoms with UF profiling, UF profiling could be incorporated into their individual clinical dialysis prescriptions.

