4 STUDY DESIGN AND ENDPOINTS

4.1 DESCRIPTION OF THE STUDY DESIGN

The study is a 4-period cross-over trial (see schematic of study design) in which participants are successively alternated between study arms across 4 periods with intervening washout periods, and treatment order is randomized. The study control arm is conventional HD: the patient's standard HD prescription (no UF profiling). The study experimental arm is conventional HD + linear UF profiling. Linear UF profiling will be specified as a linearly decreasing UF rate with a UF rate starting at 1.33 times the rate that would be needed at a constant UF rate to achieve the desired post-weight (Fresenius 2008K machine profile 2). After providing consent, patients will be randomly allocated to experimental or control treatment for period 1. Patients will undergo 9 treatments during each phase for a total of 18 conventional HD treatments and 18 UF profiled treatments. Patients will undergo 3 wash-out HD treatments between phases. The study will be double-blinded in that patients will not be informed of the treatment paradigm. Investigators, including those performing TTE interpretation, will be blinded to treatment paradigm. Ultrasonographers performing intra-HD TTEs will be blinded to treatment paradigm.

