4.2.1 PRIMARY ENDPOINT

- 1) Intradialytic hypotension: measured on a per-treatment basis; defined as nadir systolic BP <90 mmHg
- 2) Troponin T change: measured at the 7th treatment of each phase; defined as pre-HD – post-HD troponin T (ng/mL) and percentage change (troponin T rise) $\geq 10\%$
- 3) Left ventricular global longitudinal strain (GLS) on TTE: measured at baseline and 30 minutes before HD end during 7th treatment in the first phase of each treatment type (once during conventional and once during UF profiled treatment); defined as % GLS change (intradialytic GLS – baseline GLS), see Appendix A for TTE protocol. A change $\geq 2.5\%$ indicates a clinically important change in GLS.

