10.5 SAMPLE SIZE

This cross-over study is designed as a pilot study to test for efficacy signals. However, with its cross-over design in which each participant acts as his or her own control, we are powered to detect clinically and statistically significant differences across arms within patients. With a sample size of 30, we have 80% power to detect a 5.9 mmHg difference in nadir SBP (S.D. 8), a ≥ 0.07 ng/mL troponin T difference (S.D. 0.1), a 2.2% strain difference (S.D. 3), and 4% ejection fraction difference (S.D. 5); all clinically meaningful differences. We have 80% power to detect a 31% absolute difference in the binary endpoint of Troponin T change >0.1 ng/mL (event rate=20%).

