10.6 MEASURES TO MINIMIZE BIAS

10.6.1 ENROLLMENT/ RANDOMIZATION/ MASKING PROCEDURES

Randomization assignments will be generated using computer-generated random numbers. Assignments will be sealed in envelopes prior to study start. After patients consent to study participation, sealed study arm assignments will be randomly allocated to experimental or control treatment for period 1. Sequence assignments will be sealed in envelopes prior to study start and opened in a predetermined order at the start of each study period. The study will be double-blinded in that patients will not be informed of the treatment paradigm. Investigators, including those performing TTE interpretation, will be blinded to treatment paradigm. Ultrasonographers performing intra-HD TTEs will be blinded to treatment paradigm.

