Depending on the type of various endpoints, we propose to perform the following tests to test the difference between UF profile and conventional treatment.

- **Binary Outcomes**
 - We will perform repeated measure logistic regression by regressing the binary outcome on the treatment indicator and test if the coefficient before the treatment indicator is significant. Each subject will have a random intercept. The model is given by
$$\text{logit}(\text{outcome}) \sim 1 + \text{treatment} + (1|ID)$$
- **Continuous Outcomes**
 - We will perform repeated measure linear regression by regressing the continuous outcome (percentage outcome will be log-transformed) on the treatment indicator and test if the coefficient before the treatment indicator is significant. Each subject will have a random intercept. The model is given by
$$\text{outcome} \sim 1 + \text{treatment} + (1|ID)$$
- **Categorical Outcomes**
 - We will perform repeated measure multinomial regression by regressing the categorical outcome on the treatment indicator and test if the coefficient before the treatment indicator is significant. Each subject will have a random intercept. The model is given by
$$\text{multi-logit}(\text{outcome}) \sim 1 + \text{treatment} + (1|ID)$$

Quality Check

For patients who dropped out during the study, normalize endpoints to the same scale as the other patients, depending on the type of endpoints.

Sensitivity Analyses

1. Exclude participants who dropped out from all analyses.
2. Exclude participants who had endpoint data drawn "off-schedule" (troponin T, symptoms, etc.) from individual endpoint analyses.
3. Exclude participants who had an abnormality with their troponin T blood draw from troponin T-related analyses.
4. Test for difference by order of randomization (UF profiling --> conventional --> UF profiling --> conventional) vs. (conventional --> UF profiling --> conventional --> UF profiling)
5. Test for difference by clinic (site 1 vs. site 2)

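### The SAP models allow one random intercept per patient although treatment is allocated to 9-session phases, so with session-level rows the intervals for hypotension and four secondary endpoints can be too narrow

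*Combined protocol and SAP*

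**What the plan says.** The SAP (Primary Analysis) uses one model form for binary, continuous and categorical outcomes: an intercept, a treatment indicator and one random intercept per patient. The analyst is to "test if the coefficient before the treatment indicator is significant. Each subject will have a random intercept". None of the five sensitivity analyses alters the error structure. The nearest is item 4, "Test for difference by order of randomization", which concerns sequence only.

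On the design, protocol 4.1 states: "Patients will undergo 9 treatments during each phase for a total of 18 conventional HD treatments and 18 UF profiled treatments". Treatment therefore changes only between phases. Protocol 10.6.1 confirms that allocation works at that level: "Sequence assignments will be sealed in envelopes prior to study start and opened in a predetermined order at the start of each study period".

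The first-listed primary endpoint is defined for each session: "Intradialytic hypotension: measured on a per-treatment basis; defined as nadir systolic BP <90 mmHg". Section 4.2.2 defines systolic BP change, nadir systolic BP, target weight achievement and weight difference in the same way.

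The SAP does not say whether a data row is a session, a phase or a patient summary. Two places hint at summaries. The Quality Check tells the analyst, for dropouts, to "normalize endpoints to the same scale as the other patients, depending on the type of endpoints". The power statement in 10.5 ("With a sample size of 30, we have 80% power to detect a 5.9 mmHg difference in nadir SBP (S.D. 8") reproduces only with one value per patient per arm.

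The protocol names other methods: repeated-measures ANOVA or non-parametric methods for continuous outcomes (10.4.1) and GEE for binary ones (10.4.1 to 10.4.3). Neither document says which governs, and neither states a variance estimator.

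**The concern.** A single patient intercept assumes that, once a patient's overall level is removed, two sessions from the same phase are no more alike than two sessions from different phases, and that every patient has the same treatment effect. If either assumption fails, the 9 sessions of a phase carry less information about treatment than the model credits, and the treatment standard error is too small.

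Both failures are plausible. Target weight and total UF volume stay with the treating nephrologist (7.1.1, 7.1.2) and can drift between phases, as can the patient's condition. Section 2.3.2 allows for individual differences in response: "If individual participants experience improvement in UF-related cardiovascular risk or symptoms with UF profiling".

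At stake are the intervals and p-values for one primary and four secondary endpoints. Protocol 10.4.1 says this pilot will be read through its estimates and confidence intervals, so interval width matters even apart from significance.

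**Working it through.** **The plan's own figure.** A two-sample t test with 30 values per arm, SD 8, two-sided 5% and 80% power has a detectable difference of 5.88 mmHg, against the stated 5.9. With 30 × 18 = 540 session rows per arm it would be 2.80 × 8 × √(2/540) = 1.36 mmHg. The power calculation thus uses one value per patient per arm, while the endpoint definitions point to session rows.

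**Continuous endpoints, balanced layout.** Inputs: 30 patients, 4 phases, K = 9 sessions per phase (4.1, 10.5), 15 patients per sequence (assumed). Write s_e², s_ph² and s_pt² for the session, phase and patient-by-treatment variances, summing to 1 within patient. The expected mean squares are:

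- patient-by-treatment, 29 df: s_e² + 9 s_ph² + 18 s_pt²
- phase within patient and arm, 60 df: s_e² + 9 s_ph²
- session, 120 × 8 = 960 df: s_e²

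The treatment contrast varies with the first line. The SAP model on session rows pools all three (29 + 60 + 960 = 1,049 df).

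Example, phase share 0.05. The first two mean squares are 0.95 + 9 × 0.05 = 1.40. The pooled value is (89 × 1.40 + 960 × 0.95)/1,049 = 0.988. The true SE is √(1.40/0.988) = 1.19 times the model SE, an understatement of 16%.

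Example, patient-by-treatment share 0.05. The first mean square is 0.95 + 18 × 0.05 = 1.85. The pooled value is (29 × 1.85 + 1,020 × 0.95)/1,049 = 0.975, and the ratio is √(1.85/0.975) = 1.38.

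Rejection rates at nominal 5% when the average effect is zero (400,000 draws per setting; z reference for session rows, t(89) for phase means, t(29) for one row per patient per arm):

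| Excess share | True SE / SAP SE | Session rows | Phase-mean rows | One row per patient per arm |
|---|---|---|---|---|
| none | 1.00 | 5.0% | 5.0% | 5.0% |
| phase 0.02 | 1.08 | 7.0% | 5.0% | 5.0% |
| phase 0.05 | 1.19 | 10.1% | 5.0% | 5.0% |
| phase 0.10 | 1.36 | 14.9% | 5.0% | 5.0% |
| patient-by-treatment 0.02 | 1.16 | 9.2% | 7.6% | 5.0% |
| patient-by-treatment 0.05 | 1.38 | 15.5% | 10.7% | 5.0% |
| patient-by-treatment 0.10 | 1.69 | 24.7% | 14.6% | 5.0% |

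Serial correlation alone (lag-1 of 0.1, 0.2, 0.3) gives 7.1, 10.1 and 13.9% with session rows. A pattern by position in the week alone gives 4.0%, which is conservative. Correlation shared equally by all of a patient's sessions does no harm.

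**Hypotension, session rows.** Random-intercept logistic model, 5,000 null trials per setting, patient SD 1.2 logits. Event rates of 20% and 10% are assumed.

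- Phase SD 0, 0.3, 0.5, 0.7 logits: 5.1, 6.8, 8.5, 12.5% (20% rate); 4.3, 6.4, 8.4, 10.5% (10% rate).
- Patient-by-treatment SD 0.3, 0.5, 0.7 logits: 9.1, 13.6, 20.0% and 6.9, 11.6, 16.1%. These SDs are per arm; the SD of a patient's treatment effect is √2 times larger (0.42, 0.71, 0.99).
- Serial correlation alone: 4.9 to 6.9%.
- At the Bonferroni level 0.05/3 = 0.0167 and a 20% rate: 1.9, 2.6, 3.3, 5.8% over the phase SDs.

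A separate simulation with patient SD 1.5 logits (600 trials per setting) gave 3.8 to 4.3% with no excess and 8.0 to 8.5% at phase SD 0.5.

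**Other endpoints.** Symptoms, with three readings per phase, give 6.4 and 7.7% at phase share 0.05 and 0.10 (linear approximation). Troponin T and patient acceptance have one value per phase and are exposed only to patient-by-treatment variation; troponin T gives 7.0 and 8.8% at shares 0.10 and 0.20. GLS and EF, measured once per treatment type, are unaffected.

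**The case against.** The strongest reply is that the harm is not shown to exist. The SAP never says rows are sessions; how often an endpoint is measured does not define a model row, and both the Quality Check and the power figure fit summaries. With one row per patient per arm the problem disappears. That is correct, and it is why the concern is conditional. Phase-mean rows, however, remove only the phase part, and nothing in the SAP commits to the one safe unit.

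Second, every correlation and event rate is assumed. Section 7.5 says usual treatments will not change, and 7.1 keeps dialysate and medications at the baseline prescription. This limits drift from prescribing, but not drift in clinical state or target weight.

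Third, the largest rates need UF profiling to affect individuals while averaging zero. If it affects no patient, the patient-by-treatment share is zero and only phase or serial correlation counts; for hypotension the inflation is then modest at small SDs. This stands for p-values. Intervals for the average effect remain too narrow when response varies.

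Fourth, the protocol's GEE would largely settle hypotension if clustered on patient with a robust variance. It states neither, and the SAP specifies a different model. Uncorrected robust GEE with a z reference gives 5.9 to 7.6%, so the small-sample correction is worth having. GEE also estimates a population-averaged odds ratio and generally needs stronger missing-data assumptions than a likelihood model, which matters because missed sessions are not made up (5.3).

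**Conclusion.** The concern holds as a conditional defect that should be fixed. Read with session rows, the SAP models give intervals that are too narrow for hypotension and four secondary endpoints whenever sessions in a phase or arm share variation beyond the patient intercept. For continuous endpoints, a phase-level share of 5% of within-patient variance is enough to double the nominal 5% error rate. For hypotension the rate is about 6 to 7% at a phase SD of 0.3 logits and 10.5 to 12.5% at 0.7. With no excess correlation there is no inflation.

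Confidence in the size is moderate, because the row unit is unstated and the correlations are assumptions. Two defects need no assumption: the row unit and variance estimator are missing, and the protocol and SAP name different primary methods.

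**What to change.** 1. State the row unit for each endpoint.
2. For the five per-session endpoints and symptoms, take the error at patient level. For binary endpoints use GEE clustered on patient with a small-sample robust variance (for example Mancl-DeRouen) and a t reference. For continuous endpoints use the same, or a paired analysis of each patient's arm difference. GEE keeps patients who complete only one arm; the paired analysis does not.
3. If a mixed model is preferred, include both patient-by-treatment and patient-by-phase random terms. A patient-by-phase term alone still gives 7.6, 10.7 and 14.6% at patient-by-treatment shares 0.02, 0.05 and 0.10.
4. Use the same patient-level error for troponin T and patient acceptance.
5. Name one primary method and one variance estimator, identically, in protocol 10.4.1 to 10.4.3 and in the SAP, and say for binary endpoints whether the odds ratio is population-averaged or patient-specific.

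Over the settings examined, the paired analysis of continuous endpoints rejects 4.7 to 5.2% and corrected GEE for hypotension 4.5 to 5.9%. The two-term mixed model gives 4.0 to 6.0%, but was checked for linear outcomes only.

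The cost is wording and a few lines of code, with no new data. With no excess correlation, paired t(29) intervals are about 4% wider (2.045/1.960 = 1.043) and 80% power becomes 77%. At phase shares 0.02, 0.05 and 0.10 they are on average 12, 23 and 41% wider, of which 8, 19 and 36% is the correction of the standard error itself.

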4.2.2 SECONDARY ENDPOINTS

- 1) Systolic BP change: measured on a per-treatment basis; defined as pre-HD – nadir intra-HD systolic BP (mmHg)
- 2) Nadir systolic BP: measured on a per-treatment basis; defined as the minimum intradialytic systolic BP (mmHg)
- 3) Target weight achievement: measured on a per-treatment basis: defined as post-HD weight within 1 kg of prescribed target weight.
- 4) Weight difference: measured on a per-treatment basis; defined as target weight – post-HD weight (kg)
- 5) Patient acceptance: measured after treatment 9 of each phase; response to the following question, "If recommended by your physician, would you be willing to adopt the HD prescription you have received during the last 9 treatments?"

6) TTE ejection fraction (EF): measured 30 minutes before HD end during 7th treatment in the first phase of each treatment type (once during conventional and once during UF profiled treatment); defined as % EF change (baseline – intradialytic EF), see Appendix A for TTE protocol

7) Patient-reported symptoms: measured after the 1st HD treatment each week; see Appendix B for data collection form.

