4.2.3 EXPLORATORY ENDPOINTS

1) Early diastolic myocardial velocity (Em): measured 30 minutes before HD end during 7th treatment in the first phase of each treatment type (once during conventional and once during UF profiled treatment); calculated as the average of early diastolic velocities recorded at the medial and lateral mitral annulus, see Appendix A for TTE protocol

2) Tricuspid annulus systolic excursion velocity (S_t): measured 30 minutes before HD end during 7th treatment in the first phase of each treatment type (once during conventional and once during UF profiled treatment); measured as the distance of tricuspid annular movement between end-diastole to end-systole (cm), see Appendix A for TTE protocol

3) Blood volume monitor slope (by hour): measured during the 1st (last) HD treatment of each week, hour-by-hour basis; defined as change in blood volume (%) on an hourly basis

4) Blood volume monitor slope (by treatment): measured during the 1st (last) HD treatment of each week, from start to end of HD treatment; defined as change in blood volume (%) over the entire HD treatment

5) Plasma refill: measured 10 minutes before HD end during 7th treatment of each phase; defined as the percentage increase in hematocrit

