10.4.2 ANALYSIS OF THE PRIMARY EFFICACY ENDPOINT(S)

Comparisons of values for the binary primary endpoints of hypotension and troponin T rise $\geq 10\%$ between HD treatments will be performed using generalized estimating equations. Comparisons of values for the continuous

primary endpoint of global longitudinal strain change will be performed using ANOVA or non-parametric methods depending on data type.

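### The SAP's blanket log transform of percentage outcomes is undefined for zero or negative changes, including the primary GLS change, and does not match the additive scale used for power

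*Combined protocol and SAP*

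**What the plan says.** The SAP (Primary Analysis, Continuous Outcomes) gives one random-intercept linear model for all continuous endpoints, fitted by "regressing the continuous outcome (percentage outcome will be log-transformed) on the treatment indicator". It contains no list of percentage outcomes, offset, ratio form or exclusion rule.

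The protocol expresses these continuous endpoints as percentages:

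- GLS, a primary endpoint (4.2.1): "defined as % GLS change (intradialytic GLS – baseline GLS". A change of at least 2.5% "indicates a clinically important change in GLS".
- Ejection fraction, secondary (4.2.2): "defined as % EF change (baseline – intradialytic EF".
- Blood volume, exploratory (4.2.3): "defined as change in blood volume (%) over the entire HD treatment", and also hour by hour.
- Plasma refill, exploratory (4.2.3): "defined as the percentage increase in hematocrit".

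Protocol 10.4.2 says that analysis of the "primary endpoint of global longitudinal strain change will be performed using ANOVA or non-parametric methods depending on data type". It does not mention a transformation. Protocol 10.5 gives the detectable effects as "a 2.2% strain difference (S.D. 3), and 4% ejection fraction difference (S.D. 5".

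**The concern.** The GLS, ejection fraction and blood-volume changes can each be zero or negative, and such values have no logarithm. This is so whether the GLS percentage is taken as a difference in strain points or as a relative change from baseline. As written, the analyst of a primary endpoint would have to improvise once the data are in hand.

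If undefined values are dropped, which is a common software default though not something the SAP states, patients leave the comparison because of their outcome, and at different rates in the two arms. Which outcomes are lost depends on a sign convention that neither document gives. Improvements are lost if strain is recorded as negative, and worsenings are lost if it is recorded as a magnitude. If a constant is added instead, its size becomes an analysis choice that was not planned.

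There is also a mismatch of scale. The power statement and the 2.5% threshold are additive, so a treatment coefficient on the log scale cannot be read against either.

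**Working it through.** **Inputs from the documents.** Difference 2.2, SD 3, 30 participants, 80% power (protocol 10.5); two-sided 0.05 (10.4.1); one GLS change per treatment type (4.2.1), hence 60 values from 30 completers.

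**Assumptions not in the documents.** Normal changes; arm means as shown below; within-patient correlation r of 0 or 0.5.

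**1. The plan's own figure.** With 30 values per treatment, treated as unpaired, the standard error is 3 × √(2/30) = 0.775, and 2.2/0.775 = 2.84. Power is Φ(2.84 − 1.96) = 0.81, or 0.80 from the two-sample t. The stated 80% is therefore reproduced on the untransformed percentage-point scale. A paired analysis has standard error 3 × √(2(1 − r)/30), which gives 78% power at r = 0 and 97% at r = 0.5. No log-scale effect or SD is given, so the documents support no power figure for a log analysis.

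**2. Share of undefined values.** For mean change m, P(change ≤ 0) = Φ(−m/3). The mean of the values that remain after dropping is m + 3φ(m/3)/Φ(m/3). The number left out of 60 is 30 × (2 − p_control − p_UF). With worsening counted as positive:

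| Means, control / UF | Undefined, control / UF | Mean of retained values | Retained difference (true 2.2) | Values left of 60 |
|---|---|---|---|---|
| 2.2 / 0 | 23% / 50% | 3.39 / 2.39 | 1.00 | 38 |
| 4.4 / 2.2 | 7% / 23% | 4.84 / 3.39 | 1.45 | 51 |
| 6 / 3.8 | 2% / 10% | 6.17 / 4.40 | 1.77 | 56 |

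In the last row, treating values as independent, the chance of at least one undefined value is 1 − (0.977 × 0.897)^30, or about 98%.

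**3. Power if undefined values are dropped.** The SAP's random-intercept model was simulated on log(change), fitted by REML with a Wald test, keeping unpaired values (4,000 runs):

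| Means, control / UF | r = 0 | r = 0.5 |
|---|---|---|
| 2.2 / 0 | 30% | 42% |
| 4.4 / 2.2 | 50% | 67% |
| 6 / 3.8 | 63% | 82% |
| 2.2 / 0, opposite sign convention | 22% | 28% |
| Untransformed, paired (step 1) | 78% | 97% |

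Under the opposite convention 77% of control and 50% of UF values are undefined, which leaves 22 of 60.

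**4. Power if a constant is added.** Using log(x − min + k) with r = 0.5 (3,000 runs), power for k = 0.01, 1 and 10 is 74%, 95% and 97% at means 2.2/0, and 75%, 94% and 97% at 6/3.8. Taking dropping and these three offsets as four candidate analyses, they do not all agree on significance in 64% of trials at 2.2/0 and 32% at 6/3.8. With no true difference, at least one of the four is significant in 13% of trials (common mean 1.1) or 10% (common mean 4.9), against about 6% for the untransformed model.

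**5. Scale.** The same 2.2-point effect corresponds to a ratio of mean changes of 0/2.2 = 0, 2.2/4.4 = 0.50 or 3.8/6 = 0.63. A fixed additive effect has no single multiplicative equivalent.

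**The case against.** The SAP never says that GLS change is a percentage outcome, so coverage is inferred. A percentage change could also be logged as the ratio of intradialytic to baseline strain, which exists when the two share a sign. Protocol 10.4.2 names GLS and plans methods that accept negative values, so a computable analysis is available within the document set.

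On size, only the SD, the difference and the sample size come from the text. The means, the correlation and the handling rules are assumed. Offsets of 1 and 10 cost little power, and with paired t-tests they disagree with each other in only about 5% (means 2.2/0) or 4% (6/3.8) of trials. The large disagreement rates come mainly from dropping values and from the very small offset. The null rates of 13% and 10% describe picking the best of four analyses, not any one of them, and are lower with paired t-tests (8.5% and 7.7%). Finally, this is a pilot, and the binary hypotension and troponin-rise analyses are unaffected.

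The points about assumptions stand and limit what the figures can show. The others do not rescue the text. Among primary and secondary endpoints, the percentages are GLS change, ejection fraction change and troponin T percentage change, the last of which 10.4.2 analyses as a binary rise. If GLS and ejection fraction are excluded, the clause has almost nothing there to apply to. Protocol 4.2.1 defines GLS change as a difference, and the SAP mentions no ratio. Section 10.4.2 is silent on transformation and neither document says which governs, so it adds a conflict without resolving one. The lower null rates reflect a different test from the model the SAP specifies. Pilot status does not make an undefined transformation of a primary endpoint computable.

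**Conclusion.** The concern holds and needs correcting before analysis. On the natural reading, the log rule cannot be applied to GLS change without an unplanned choice, and it departs from the additive scale on which the stated 80% power is reproduced. The mismatch of scale does not depend on any assumed mean.

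The numerical consequences do depend on assumptions. For Normal changes with SD 3 and the three pairs of means with worsening positive, dropping undefined values shrinks the retained difference from 2.2 to between 1.0 and 1.8 points. Power falls to 30–63% at r = 0 and 42–82% at r = 0.5, and is lower still under the opposite sign convention. With an added constant the loss ranges from almost nothing to more than 20 percentage points, depending on the constant. The documents do not fix where in these ranges the trial would fall.

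**What to change.** Delete the general instruction to log-transform percentage outcomes. State that GLS, ejection fraction, blood-volume and plasma-refill changes are analysed untransformed, in percentage points, in the random-intercept model already specified. A rank-based or bootstrap analysis can serve as a check for skewness. Limit logs to named, strictly positive quantities; the post-HD to pre-HD troponin T ratio would be one. State whether strain is recorded as negative or as a magnitude, and which direction of change is worsening. Align the SAP with protocol 4.2.1, 10.4.2 and 10.5, and say which document governs the analysis.

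If a relative scale is preferred for GLS, a pre-specified log ratio of intradialytic to baseline strain magnitude can be computed. The power statement and the 2.5% threshold would then have to be restated on that scale.

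The cost is a few lines of SAP text, with no change to data collection, participants or trial conduct.
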